2. SCOPE

The COOL-AMI EU Pivotal Trial Statistical Analysis Plan defines the detailed specifications for the analysis of the clinical trial data.

3. REFERENCE

None

4. REQUIREMENTS

4.1 Clinical trial data shall remain confidential per HIPAA and applicable European Regulations.

4.2 Clinical trial data will be maintained in the Clinical Affairs files.

5. APPENDICES

5.1 Appendix A – Statistical Analysis Plan26 pages

6. REVISION HISTORY

Rev.	Description	Originator	Effective Date
1	Document was initially released in CT system # CT01-030 AMI EU Pivotal Trial – Statistical Analyses Plan on 16 June 2017	[name]	10/01/2018
2	Revised header and format to comply with ZeDS formatting. Edited to account for suspension of trial	[name]	See signature page

EDC-4044

TH	Therapeutic hypothermia
TVR	Target vessel revascularization

2 Introduction

The Statistical Analysis Plan provides prospective, detailed specification for the analyses for **Cool-AMI EU Pivotal Trial: A Multicenter, Prospective, Randomized-Controlled Trial To Assess The Safety And Effectiveness Of Cooling As An Adjunctive Therapy To Percutaneous Intervention In Patients With Acute Myocardial Infarction (EDC 3135)**. The background and objectives of the document is a reiteration of the study protocol supplemented with additional details as appropriate. This document will support protocol and associated amendments updated throughout the life of the study. It was finalized upon completion of study closeout before database lock.

2.1 Background

Coronary heart disease complicated by acute myocardial infarction (AMI) remains a leading cause of death and disability worldwide. AMI most commonly occurs when a coronary artery becomes occluded by thrombus following the rupture of an atherosclerotic plaque. Factors that may affect the size of the subsequent infarction include duration of ischemia, size of ischemic territory, collateral blood flow, and myocardial metabolic rate. Long-term sequelae of AMI include ventricular remodeling, loss of ventricular function, congestive heart failure, dysrhythmias, and sudden death.

Although major gains have been made in improving the outcome of patients suffering AMI, and early myocardial reperfusion with the use of thrombolytic therapy or primary percutaneous coronary intervention (PCI) are effective, morbidity and mortality remain substantial. This may be because restoration of blood flow to the ischemic myocardium can itself induce injury through myocardial “ischemia reperfusion injury” (IRI), which can be defined as that portion of the ischemia-reperfusion

continuum which is preventable by treatment initiated after restoration of blood flow¹. It has been proposed that 50% of the final infarct size may be a function of IRI¹.

Ischemia reperfusion injury is protean in its components, likely including free radical and reactive oxygen species, disordered vasculature, inflammatory injury, programmed cell death, and pathologic remodelling among others². Unfortunately, the cascading nature of these events challenge and, in the end, may defeat the single molecular target pharmacologic model. The long list of failed IRI pharmacologic agents includes antioxidants, calcium channel blockers, anti-inflammatory drugs, sodium hydrogen exchange inhibitors, among others, has led some to question the importance of reperfusion injury in the myocardium³.

Therapeutic hypothermia (TH) has been studied for many years as a potential therapy for ischemia and reperfusion^{4,5,6,7,8,9,10}. The past few years have seen development of a broad literature reporting both laboratory and clinical trials of mild post-reperfusion TH in the treatment of disease entities as diverse as acute cardiac arrest, stroke, and myocardial infarction, among others. Unlike single pharmacologic agents, TH has the potential to modify and ameliorate multiple pathways of injury.

2.2 Purpose of the analyses

The objective of this randomized clinical trial is to evaluate the safety and effectiveness of therapeutic hypothermia, using the ZOLL Proteus IVTM System, as an adjunctive therapy for patients presenting with acute anterior myocardial infarction and undergoing PCI, in comparison with patients with acute anterior myocardial infarction and undergoing PCI only.

3 Study Objectives and Endpoints

3.1 Study Objectives

This is a confirmatory trial to evaluate safety and effectiveness of therapeutic hypothermia using ZOLL Proteus IVTM System for patients with acute anterior MI in comparison with anterior MI patients who only undergo PCI. Efficacy is established by demonstrating a relative reduction of 20% in mean anterior myocardial infarct size (IS), as determined by Cardiac Magnetic Resonance (cMR) imaging at 4-6 days post infarct in the Test Arm (cooling + PCI) compared to the Control Arm (PCI only). Infarction Size (IS) is defined as % Left Ventricular Mass as measured by Cardiac Magnetic Resonance (cMR) imaging.

Infarct Size (IS) will be assessed by Cardiac Magnetic Resonance (cMR) at 4 – 6 days following the index procedure and is a measurement of “myocardial reperfusion injury” by a Core Lab.

The trial is considered to have met the primary efficacy endpoint if the Test Arm demonstrates a 20% relative reduction in mean infarct size (defined as a 3.5% absolute reduction) compared to the Control Arm.

Furthermore, safety will be evaluated throughout the trial on basis of non-inferiority, with 6% established as the margin of non-inferiority.

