12 lead ECG	X										
Adverse Events		X	X	X	X	X	X	X	X	X	
Catheter Access Site Assessment						X	X	X			
Cardiac Magnetic Resonance (cMR) imaging								X			
NYHA Assessment									X	X	
KCCQ Assessment									X	X	

COPY

5 Sample Size

Sample size considerations are based on both the primary effectiveness analysis.

The primary effectiveness analyses is designed to detect a relative reduction of 20% in mean anterior myocardial infarct size (IS), as determined by Cardiac Magnetic Resonance (cMR) imaging at 4-6 days post infarct in the Test Arm (cooling + PCI) compared to the Control Arm (PCI only). The absolute magnitude of a relative reduction of 20% depends on the mean IS in the control arm, which is assumed to be approximately 17 %LV. Therefore, the treatment effect of interest is an absolute difference of 3.5 %LV. Therefore, the treatment effect of interest is an absolute difference of 3.5 %LV.

The null hypothesis is that the mean IS in the Test Arm is equal to the mean IS in the Control Arm. The assumed standard deviation is 12 %LV and the final analysis will be conducted using a two-sided test at the alpha=0.044 level of significance (adjusted for the two interim analyses). Based on these assumptions, the required total sample to detect a mean difference of 3.5 %LV with 80% power is 384 subjects (192 subjects per group). Allowing for a potential dropout rate of 24%, the planned total sample size is 500 subjects (250 subjects per group).

$$H_0: \mu_T = \mu_C$$

$$H_A: \mu_T \neq \mu_C$$

Null hypothesis:

The null hypothesis is that the mean IS in the Test Arm is equal to the mean IS in the Control Arm.

Alternative hypothesis:

The mean %LV in the control arm is not equal to mean of control arm.

This 20% relative reduction is defined as absolute value 3.5 %LV and accounted for in our sample size calculation as treatment effect. This assumption is based on previous studies with anterior infarct size measured with cMR reporting between 17-20% absolute %LV in anterior infarct (**Tables 1 & 2**). Therefore, a relative reduction of 20% can vary depending on the mean infarct size of the control arm. Assuming a representative mean infarct size of ~17% in controls, we assume absolute difference of 3.5 %LV is equivalent to 20% mean anterior infarct size would be an adequate detection limit for effect.

COPY

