Table 1: Clinical trials reporting anterior mean infarct size measured by cMR 4-6 days in PCI trials (Control Group Only) and calculated 20% relative reduction

Study name	Anterior n	Mean infarct size	Standard Deviation	20% relative reduction
APEX-AMI³⁷	60	16.6	10.7	3.3
LIPSIAABCIXIMAB³⁸	63	25.3	16.1	5.1
LIPSIA-STEMI³⁹	38	18	16.0	3.6
CRISP-AMI^{40*}	142	37.5	20.1	7.5
INFUSE-AMI⁴¹	172	17.3	10.2	3.5
RAPID-MI ICE¹	7	19.7	8.5	3.9
CHILL-MI³³	21	26.5	10.9	5.3
AMI EU PILOT	21	23.3	12.0	4

*>60% are large proximal infarcts

COPY

Table 2: Hypothermia trials using cMR measured infarct size as primary outcome

	RAPID-MI ICE (2009)	CHILL-MI (2013)	AMI EU Pilot (2017)	Pooled AMI EU Pilot, RAPID-MI-ICE, CHILL-MI
n (Control vs Cooled)	7 vs 5	21 vs 15	21 vs 19	49 vs 39
Control Mean LV%	19.7	26.5	23.3	24.5
20% reduction in infarct	3.94	5.3	4.7	4.9
Std Dev (control)	8.5	10.9	12.0	10.5
Std Dev (cooled)	6.5	9.3	10.3	11.0

The potential impact of variations in control infarct size and variability is presented in **Table 3**.

Table 3: Sample size estimates with alternative standard deviation and detection limit

Mean Difference in infarct size for detection (%)	Standard Deviation	Estimated Sample Size	Total Enrolment (with 20% drop-out)
3.0	9	288	360
3.0	10	355	444
3.0	11	430	534
3.0	12	506	636
3.5	9	212	264
3.5	10	260	330
3.5	11	314	396
3.5	12	374	468
4.0	9	162	204
4.0	10	200	252
4.0	11	240	300
4.0	12	286	360

The safety endpoint is a composite endpoint. In consideration regarding power of this study, expected incidence is based on a literature review of acute MI hypothermia trials that combined six studies: Dixon et al, COOL MI, ICE-IT, RAPID MI-ICE, CHILL-MI, VELOCITY¹¹ which resulted in a 30-day MACE rate of 6.6% in the Control patients and 7.5% in treatment patients. Previously, AMIHOT II trial defined 30-day MACE rate comprised of death, reinfarction, target vessel revascularization, and stroke used a non-inferiority hypothesis with a 6% equivalence delta and 7% in the Control patients¹².

The hypothesis for the primary safety endpoint is the following:

$$H_0: \pi_T \geq \pi_C + 6\%$$

$$H_A: \pi_T < \pi_C + 6\%$$

π_T and π_C are the underlying proportion of patients having a MACE event.

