6.7 Multiple Testing

For this trial, there is only one primary effectiveness outcome with two interim analyses. Overall significance value is preserved for interim analyses with established stopping rules preserving the overall type 1 error rate of alpha for <0.05.

For primary and secondary safety analyses, given the number of statistical tests, adjustment for multiplicity is considered counterproductive for considerations of safety as there is no control of the type I error for a single hypothesis. Tests will be conducted using one-sided test at alpha 0.05 level of significance.

All other analyses will be conducted using two-sided tests at the alpha=0.05 level of significance.

7 Summary of Study Data

[figure not shown]
Data will be sorted by treatment and centre and structured with columns for Test and Control. Descriptive and efficacy figures and tables will be produced for ITT and PP population. All

continuous variables will be summarised using the following descriptive statistics: n (non-missing sample size), mean, standard deviation, median, maximum and minimum. The frequency and percentages (based on the non-missing sample size) of observed levels will be reported for all categorical measures. In general, all tables will be annotated with population size relevant to the table/treatment, including any missing observations.

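### SAP Section 3.1 makes primary efficacy success depend on demonstrating a 20% (3.5 %LV) reduction, but Sections 5 and 8.1 test and power only equality of means

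*SAP*

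**What the plan says.** Section 3.1 calls the trial confirmatory and states the efficacy criterion twice. The first statement is "Efficacy is established by demonstrating a relative reduction of 20% in mean anterior myocardial infarct size (IS"). The second is written as a decision rule: "The trial is considered to have met the primary efficacy endpoint if the Test Arm demonstrates a 20% relative reduction in mean infarct size", with the reduction defined as 3.5% absolute. No other section says when the primary efficacy endpoint is met.

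Section 5 sets up a different question. Its hypothesis is equality: "The null hypothesis is that the mean IS in the Test Arm is equal to the mean IS in the Control Arm". The final analysis is a "two-sided test at the alpha=0.044 level of significance (adjusted for the two interim analyses"), and "the required total sample to detect a mean difference of 3.5 %LV with 80% power is 384 subjects". The 20% reduction appears there as a planning quantity, "accounted for in our sample size calculation as treatment effect".

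Section 6.7 refers to "established stopping rules preserving the overall type 1 error rate of alpha for <0.05", which concerns the interim and final significance tests. Section 8.1 gives summary statistics and a two-sided p-value from a t-test or a Wilcoxon rank-sum test, chosen after a look at normality. It contains no 20% or 3.5 %LV threshold.

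**The concern.** A rule that requires a 20% reduction to be demonstrated is not a rule that requires the hypothesis of no difference to be rejected. To demonstrate 3.5 %LV could mean observing a mean reduction of at least 3.5, or showing statistically that a smaller reduction is excluded. Section 5 tests neither, and its 80% power applies to neither.

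The verdict on the only primary effectiveness outcome is at stake. A significant reduction smaller than 3.5 %LV is a success by Section 5 and a failure by Section 3.1. In a small trial, a non-significant reduction of 3.5 %LV could be called a success if Section 3.1 is read as a bare point-estimate rule. Investigators and subjects are not blinded, so leaving the rule open allows the reading to be chosen once results are known.

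**Working it through.** **Inputs (Section 5):** difference 3.5 %LV, SD 12 %LV in both arms, two-sided alpha 0.044, power 80%, 192 per arm, control mean about 17 %LV. Alternative SDs of 9, 10 and 11 come from Table 3.

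**1. The plan's own figure.** For a test of equality, n per arm = 2·SD²·(z₀.₉₇₈ + z₀.₈₀)²/δ² = 2·144·(2.014 + 0.842)²/3.5² ≈ 192, or 384 in total. Power at 192 per arm is 80.1% by the normal formula and 79.8% by the noncentral t. The figure reproduces, and both formulas take a null difference of zero.

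**2. Where significance starts.** SE = 12·√(2/192) = 1.225. Critical difference = t(0.978; 382 df)·1.225 = 2.475 %LV, about 14.6% of a control mean of 17.

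**3. Chance of success at a true 3.5 %LV, 192 per arm, SD 12.**

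| Rule | Chance of success | True reduction needed for 80% |
|---|---|---|
| Equality test (Section 5) | 79.8% | about 3.5 |
| Observed reduction ≥ 3.5 | 1 − Φ(0) = 50% | 3.5 + 0.8416·1.225 = 4.53 |
| Lower 95.6% confidence limit above 3.5 | P(observed > 3.5 + 2.475) = 2.2% | 3.5 + 2.475 + 0.8416·1.225 ≈ 7.01 (7.01/17 = 41%) |

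Requiring significance as well leaves the second row unchanged, because 3.5 already exceeds 2.475.

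**4. Size of the disagreement.** The chance of a significant result with an observed reduction below 3.5 is 79.8% − 50% ≈ 30%. At 192 per arm with SD 11, 10 and 9 it is 36%, 42% and 46% by simulation.

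**5. Smaller trials.** The number per arm at which an observed 3.5 just becomes significant at 0.044 is:

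| SD | n per arm | Critical difference |
|---|---|---|
| 9 | 55 | 3.498 |
| 10 | 68 | 3.487 |
| 11 | 82 | 3.487 |
| 12 | 97 | 3.493 |

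Above that number a result can be significant and still fall short of 3.5. Below it, every significant t-test reduction exceeds 3.5, and the remaining conflict is an observed 3.5 that is not significant. The Wilcoxon option has no such cut-off on the mean difference.

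**6. Relative against absolute form.** 20% of 17 is 3.4, and 3.5 is exactly 20% only at a control mean of 17.5. At the control means of 23.3 and 24.5 in Table 2, 3.5 %LV is 15.0% and 14.3%, while 20% would be 4.7 and 4.9. Read as a success rule, the two forms in Section 3.1 can therefore disagree.

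**The case against.** The strongest reply is that Section 5 settles the matter. It gives the 20% reduction its role as the treatment effect in the sample size calculation, states equality of means in words and symbols, and is followed by a single p-value in Section 8.1. On that view Section 3.1 is only loose wording. This is the likeliest intent, but Section 5 does not withdraw the rule in Section 3.1, which is worded as a success criterion. For safety, the same SAP writes its 6% margin into the hypothesis and states the decision rule, so the lack of any link for efficacy is a real gap.

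Several narrower points stand:

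- The confidence-limit reading has little textual support, since no efficacy margin is set. Its 2.2% and 7.0 %LV show only what that reading would imply.
- The 50% holds for any symmetric estimator whose true effect equals the threshold, whatever n or SD. It shows that a point-estimate rule cannot have the stated 80% power.
- The 30% belongs to the planned design. The revision history records a suspension of the trial, and Section 6.4 says enrolment was never completed. At SD 12 the critical difference is 3.51 at 96 per arm, 3.85 at 80 and 4.46 at 60, so the zone of significant results below 3.5 may be empty in the analysis actually run.
- Replacing the stricter written rule with the looser one after closeout of an unblinded trial needs care. The sponsor's intent should be established and recorded first.

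These points limit the size of the effect on the actual analysis. They do not reconcile Section 3.1 with Sections 5 and 8.1.

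**Conclusion.** The concern holds. Section 3.1 gives the only success criterion for primary efficacy, and it is not the hypothesis that Section 5 tests and powers or that Section 8.1 analyses. Under the planned design (192 evaluable per arm, SD 12, alpha 0.044, t-test, true reduction 3.5 %LV), the 80% power falls to 50% or 2.2% under the two readings of Section 3.1, and about 30% of trials would get opposite verdicts from the two sections. The SAP does not give the final evaluable number, so the probability of conflict in the actual analysis is unknown. The contradiction in the success rule exists at any sample size.

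**What to change.** Establish and record which rule was intended. If 3.5 %LV was the planning effect, as Section 5 suggests:

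- Replace both sentences in Section 3.1 with a rule such as: *Primary efficacy is met if the primary two-sided test of infarct size in the ITT set is statistically significant in favour of the Test Arm at alpha 0.044.* Add that 20%, or 3.5 %LV, is the planning effect from Section 5.
- Name in Section 8.1 the single test that decides.
- Add a 95.6% confidence interval for the mean difference to the Infarct Size figure, which already lists absolute and relative differences. This interval matches alpha 0.044 if the t-test is the deciding test. The 0.044 is adjusted for two interim analyses, and the SAP does not say whether both were held, so confirm that level and let the interval follow it.

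The 384 subjects and 80% power then stand as statements about the planned design.

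If a 3.5 %LV threshold is truly intended, say whether it applies to the point estimate or to the confidence limit, and whether the absolute or the relative form governs. Restate the power at a true 3.5 %LV with 192 per arm: 50% for the point estimate or 2.2% for the confidence limit.

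The cost is two sentences in Section 3.1 and one line in Section 8.1, with no new data and no change to the sample size. Because the SAP was finalized at closeout of an unblinded trial, issue the change before database lock as a documented revision with its reason. Section 2 says the objectives repeat the protocol, so make the same edit there if it carries this wording.

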3.2 Endpoints

Primary Effectiveness Endpoint:

Mean anterior myocardial infarct size (IS), as determined by Cardiac Magnetic Resonance (cMR) imaging at 4-6 days post infarct in the Test Arm (cooling + PCI) compared to the Control Arm (PCI only). Infarction Size (IS) is defined as % Left Ventricular Mass as measured by Cardiac Magnetic Resonance (cMR) imaging. Infarct Size (IS) will be assessed by Cardiac Magnetic Resonance (cMR) at 4 – 6 days following the index procedure.

Primary Safety Endpoint:

Per-patient rate of composite Major Adverse Cardiac Events (MACE) subjects, defined as Cardiac Death (CD), All Myocardial Infarction (all MI) and Clinically-Indicated Target Vessel Revascularization (CI-TVR) at 30 days; non-inferiority to the control.

Additional Safety Endpoints:

The following clinical components of MACE will be evaluated for per-patient rate at 30 days:

- Death (Cardiac, Vascular, Non-Cardiovascular)
- Myocardial Infarction (MI)
 - Attributable to target vessel (TV-MI)
 - Not attributable to target vessel (NTV-MI)
- Target Vessel Revascularization (TVR)
 - Clinically-indicated TVR
 - Not clinically-indicated TVR
- All coronary revascularization
- Stent Thrombosis
 - Timing (Acute, Sub-acute)
 - Evidence (Definite and Probable)

3.3 Derived variables

All endpoints will be in case report form (CRF) except for MACE event, which will be derived according to the following:

MACE event is a composite variable considered as any of the following events: Cardiac Death (CD), All Myocardial Infarction (all MI) and Clinically-Indicated Target Vessel Revascularization (CI-TVR).

4 Study Methods

4.1 General Study Design and Plan

A multicenter, prospective, interventional, randomized-controlled trial. Randomization will be in a 1:1 ratio, Test Arm (PCI + Cooling) or Control Arm (PCI alone). This is an unblinded trial with randomization using stratified by site using permuted blocks.

Subjects will be screened and randomized according to the following flow diagram:

[figure not shown]

Figure 1 Screening and Enrolment Flow

COPY

Follow-up after randomization (post-procedure, either Control with PCI only, or Test with PCI and Cooling) are described below:

[figure not shown]

Figure 2 All Patient Procedures

4.2 Inclusion-Exclusion Criteria and General Study Population

4.2.1 Inclusion Criteria:

All Inclusion Criteria must be answered YES for subject to satisfy Inclusion Criteria:

1. The patient is ≥ 18 years of age.
2. The patient must have symptoms consistent with AMI (i.e. chest pain, arm pain, etc.) and unresponsive to nitroglycerin, with symptoms beginning greater than 30 minutes but less than 6 hours prior to presentation at hospital.
3. Qualifying Infarct location:

Roll-In subjects: Evidence of Acute Anterior or Inferior MI with ST- segment elevation of ≥ 0.2 mV in two or more anterior or inferior contiguous precordial leads (V1 –V4).

Randomized subjects: Evidence of Acute Anterior MI only with ST-segment elevation of ≥ 0.2 mV in two or more anterior contiguous precordial leads.

4. The patient is eligible for PCI.
5. The patient is willing to provide written informed consent to participate in this clinical trial.

4.2.2 Exclusion Criteria:

All Exclusion Criteria must be answered NO for subject to satisfy Exclusion Criteria:

1. The patient has had a previous Myocardial Infarction.
2. The patient is experiencing cardiogenic shock (systolic blood pressure [SBP] <100 mmHg, HR >100 bpm and arterial oxygen saturation (pulse oximetry) $\leq 95\%$ without additional oxygen
3. The patient is presenting with resuscitated cardiac arrest, atrial fibrillation, or Killip risk stratification class II through IV.

4. The patient has an aortic dissection or requires an immediate surgical or procedural intervention other than PCI.
5. The patient has known history of Congestive Heart Failure (CHF), hepatic failure, end-stage kidney disease or severe renal failure (clearance < 30ml/min/1.73m²).
6. The patient is febrile (temperature > 37.5 °C) or has experienced an infection with fever in the last 5 days.
7. The patient has a known previous CABG.
8. The patient has a known recent stroke within 90 days of admission.
9. Cardio-pulmonary decompensation that has occurred en route to the hospital or, in the opinion of the physician, that is imminent or likely to occur following presentation to the clinical site.
10. Contraindications to hypothermia, such as patients with known hematologic dyscrasias which affect thrombosis (e.g., cryoglobulinemia, sickle cell disease, serum cold agglutinins) or vasospastic disorders (such as Raynaud's or thromboangiitis obliterans). The patient has a known hypersensitivity or contraindication to aspirin, heparin, or sensitivity to contrast media, which cannot be adequately pre-medicated.
11. Any contraindication to cardiac MRI, or any implant in the upper body which may cause artifacts on cardiac MRI imaging.
12. The patient has a known hypersensitivity or contraindication to aspirin, heparin, or sensitivity to contrast media, which cannot be adequately pre-medicated.
13. The patient has a known history of bleeding diathesis, coagulopathy, cryoglobulinemia, sickle cell anemia, or will refuse blood transfusions.
14. The patient has a height of <1.5 meters (4 feet 11 inches).
15. The patient has a known hypersensitivity or contraindication to buspirone hydrochloride or Pethidine (Meperidine) and/or has been treated with a monoamine oxidase inhibitor in the past 14 days.
16. Patient has a known history of severe hepatic or renal impairment, untreated hypothyroidism, Addison's disease, benign prostatic hypertrophy, or urethral stricture that in the opinion of the physician would be incompatible with Pethidine administration.
17. The patient has an Inferior Vena Cava filter in place (IVC).
18. The patient has a pre-MI life expectancy of <1 year due to underlying medical conditions or pre-existing co-morbidities.
19. The patient has a known, unresolved history of drug use or alcohol dependency, or lacks the ability to comprehend or follow instructions.
20. The patient is currently enrolled in another investigational drug or device trial.
21. The patient is apprehensive about or unwilling to undergo the required MRI imaging at follow-up, has a documented or suspected diagnosis of claustrophobia, or has Gadolinium allergy, or is in permanent Atrial Fibrillation.
22. The patient has received thrombolytic therapy en-route to the hospital.
23. The patient shows clinical evidence of spontaneous reperfusion as observed symptomatically and/or from baseline ECG findings (partial or complete ST resolution in baseline ECG prior to informed consent and randomization).
24. The patient is a vulnerable subject, for instance, a person in detention (i.e., prisoner or ward of the state).
25. The patient is a female who is known to be pregnant.

COPY

